2.7.4 Other safety data

2.7.4.1 ECG

All ECG data will be listed by treatment group, participant and visit/time; abnormalities will be flagged. Summary statistics will be provided by treatment and visit/time.

The number and percentage of participants with notable ECG values will be presented as follows:

- OT, OTcF
 - New value of > 450 and ≤ 480 ms
 - New value of > 480 and ≤ 500 ms
 - New value of > 500 ms
 - Increase from baseline of > 30 ms to < 60 ms
 - Increase from baseline of > 60 ms
- HR
 - Increase from baseline >25% and to a value > 100 bpm
 - Decrease from baseline >25% and to a value < 50 bpm
- PR
 - Increase from baseline >25% and to a value > 200 ms
 - New value of > 200 ms
- QRS
 - Increase from baseline >25% and to a value > 110 ms
 - New values of QRS > 110 ms

ECG data will be summarized by presenting summary statistics of observed data and change from baseline by treatment and timepoint. The definition of baseline is provided in Section 2.1.1.

A listing will be provided for participants with any notable values (defined above). If there is any notable value of an ECG for a participant, all measurements of this ECG value for the participant will be presented in this listing with the notable values flagged. A listing will also be provided of ECG findings for which there is a clinically significant ECG abnormality.

2.7.4.2 Vital signs

All vital signs data will be listed by treatment, participant, and visit/time and if ranges are available, abnormalities (and relevant orthostatic changes) will be flagged. Summary statistics will be provided by treatment and visit/time.

The following parameters were collected: height (cm), weight (kg), body temperature (°C), pulse rate (beats per minute), systolic and diastolic blood pressure (mmHg).

Weight, pulse rate, systolic and diastolic blood pressure will be summarized by presenting summary statistics of raw data and change from baseline by treatment and timepoint.

A listing will be provided for participants with any notable values (defined below). If there is any notable value of a vital sign for a participant, all measurements of this vital sign for the participant will be presented in this listing with the notable values flagged.

Notable criteria (High/Low):

- Systolic blood pressure [mmHg]: >140/<90 mmHg
- Diastolic blood pressure [mmHg]: >90/<50 mmHg
- Pulse rate [bpm]: >90/<45 bpm
- Weight [kg]: >120/<50 kg
- Temperature [°C]: >37.5/<35 °C

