Vital signs	Vital signs include BP and pulse measurements, and temperature. After the participant has been sitting for five minutes, with back supported and both feet placed on the floor, systolic and diastolic blood pressure will be measured three times using an automated validated arm device, e.g. OMRON, with an appropriately sized cuff. The repeat sitting measurements will be made at 1 - 2 minute intervals and the mean of the three measurements will be used. In case the cuff sizes available are not large enough for the participant's arm circumference, a sphygmomanometer with an appropriately sized cuff may be used.
Height and weight	Height in centimeters (cm) and body weight (to the nearest 0.1 kilogram (kg) in indoor clothing, but without shoes) will be measured as specified in Table 8-1 (under 'Vital signs and body measurements')

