**Table 17-1 Key Information on canakinumab**

canakinumab	
Reference	IB
Drug type	Human monoclonal antibody
Half-life	26 days
Five half-lives	130 days
Generic name	Canakinumab
Formulation	Subcutaneous
Maximal planned clinical dose	300 mg q4 weeks
Target	Anti-human interleukin-1 $\beta$ (IL-1 $\beta$ ) antibody
Pharmacology	Blocks the interaction of IL-1 $\beta$ with the IL-1 receptor (IL-1R), leading to inhibition of its downstream targets, thereby preventing IL-1 $\beta$ -induced gene activation and the production of inflammatory mediators.

canakinumab	
Metabolism	Elimination pathways for the IgG-type mAbs such as canakinumab are distinct from metabolic pathways of small molecules. The IgG-based molecules are cleared from the body by a combination of processes such as proteolysis by the liver, elimination by the reticuloendothelial system (RES) and nonspecific endocytosis.
Potential to interact with other drugs based on in vitro studies	No study was conducted with canakinumab or its mouse surrogate, 1BSUR, to investigate drug-drug interaction in non-clinical species.
Reference safety information (RSI)*	System organ classes (SOCs) in the reference safety information tables as of the latest IB include infections and infestations across all indications below, in addition to the following:  CAPS: 

• Nervous system disorders

 Periodic fever syndromes 

• Investigations (platelet count decreased)

 SJIA: 

• Gastrointestinal disorders

• Immune system disorders

• Investigations (transaminases increased, platelet count decreased, neutrophil count decreased, white blood cell count decreased)

 Oncology: 

• Investigations (blood creatine phosphokinase increased)

• Blood and lymphatic system disorders

 Gouty arthritis and Cardiovascular risk reduction: 

• No additional SOCs

 Based on similarities of the patient population with Alzheimer's disease (including elderly, hypertensive, diabetes, cardiovascular disease, chronic obstructive pulmonary disease), the RSI Table 6-5 from the Cardiovascular risk reduction program (CANTOS) will be used as the RSI table for this study.

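### The notable vital-sign rule in SAP 2.7.4.2 ignores baseline and feeds only a listing, so no output counts, by arm, the participants who became abnormal on treatment

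*SAP*

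**What the plan says.** SAP 2.7.4.2 gives each of five vital signs one high and one low limit. For blood pressure these are "Systolic blood pressure [mmHg]: >140/<90 mmHg" and "Diastolic blood pressure [mmHg]: >90/<50 mmHg". The others are pulse above 90 or below 45 bpm, weight above 120 or below 50 kg, and temperature above 37.5 or below 35 °C. None has a baseline or new-value condition. A participant who meets any limit enters a listing, in which "all measurements of this vital sign for the participant will be presented in this listing with the notable values flagged". No table of counts is planned.

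The same section plans summaries by arm and timepoint, of observed values and of change from baseline, for weight, pulse, systolic and diastolic pressure. Temperature has notable limits but is not in that change-from-baseline sentence. The section also promises that "abnormalities (and relevant orthostatic changes) will be flagged", as does Protocol 12.5.2. Protocol 8.4 has blood pressure measured "After the participant has been sitting for five minutes, with back supported and both feet placed on the floor"; the repeats are also sitting, and the mean of three is used.

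Three other parts of the SAP matter:
- **SAP 2.7.4.1 (ECG)** uses new-value and change-from-baseline criteria, and "The number and percentage of participants with notable ECG values will be presented as follows", in addition to a listing.
- **SAP 2.1.1** generally leaves unscheduled and repeat assessments out of descriptive summaries. For analyses of abnormal or worst post-baseline values it includes all of them.
- **SAP 2.1** includes minimum and maximum in the default summary of continuous data.

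**The concern.** A fixed limit describes a participant's state, whereas a safety comparison needs to know whether that state changed after dosing. Without a baseline term, the flag mixes long-standing values with emergent ones. Without a count by arm, the reader must sort them by hand. Safety is a key secondary objective (SAP 2.6). Participants may be up to 90 years old, and Protocol Table 17-1 likens them, in choosing a reference safety table, to a population that includes hypertensive patients. With 34 participants randomised (SAP 1.1), participant-level outputs carry much of the safety information.

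The orthostatic wording raises a separate question: it promises a flag for which the two documents specify no standing or supine reading.

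**Working it through.** The plan states no figure for this rule, so there is none to reproduce. The check is a comparison of sections, followed by an illustration.

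**1. The same quantity under two rules.** On ECG, a high heart rate is notable if it rises more than 25% from baseline and exceeds 100 bpm. As pulse, it is notable above 90 bpm whatever the baseline. A participant steady at 92 bpm (change 0%) is never notable under the first rule and always notable under the second.

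**2. Weight.** A fall from 75 to 60 kg is −15 kg, or −15/75 = −20%. Both values lie between 50 and 120 kg, so nothing is flagged. A participant steady at 48 kg is flagged at every visit with a change of zero.

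**3. What the other outputs recover.** At a scheduled visit, the −15 kg would be at or inside the minimum of the change-from-baseline summary, and it would appear in the full vital-sign listing. Three things are still missing by arm:
- changes seen only at unscheduled visits, which the summaries generally exclude;
- change from baseline in temperature, although infection is the first selected risk in Protocol Table 17-1;
- the number of participants who became abnormal, which means and extremes by visit do not give.

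**4. Illustration for systolic pressure with no drug effect.** The assumptions, none of them in the documents, are a person mean ~ N(μ, SD between) plus an independent visit error ~ N(0, SD within), and complete follow-up. There is one baseline and seven later Cohort 1 visits (Days 29, 57, 85, 113, 141, 171 and 281), with 400,000 simulated participants per row. The last column takes 34/2 = 17 per arm.

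| μ | SD between / within | Baseline >140 | Any later >140 | Newly >140 | Flagged later, already >140 at baseline | Flagged of 17 |
|---|---|---|---|---|---|---|
| 125 | 10 / 8 | 12% | 35% | 25% | 29% | 6.0 |
| 125 | 13 / 10 | 18% | 46% | 30% | 35% | 7.8 |
| 130 | 10 / 8 | 22% | 53% | 33% | 37% | 9.0 |
| 130 | 13 / 10 | 27% | 60% | 34% | 42% | 10.1 |
| 135 | 10 / 8 | 35% | 70% | 37% | 48% | 11.9 |
| 135 | 13 / 10 | 38% | 72% | 36% | 50% | 12.3 |
| 140 | 10 / 8 | 50% | 83% | 35% | 58% | 14.2 |
| 140 | 13 / 10 | 50% | 83% | 34% | 59% | 14.1 |

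Hand check of the baseline column, first row: 1 − Φ((140 − 125)/√(10² + 8²)) = 1 − Φ(15/12.81) = 1 − Φ(1.17) = 0.12.

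The newly-above-140 share is itself 25-37% with no drug effect, or 0.25 × 17 = 4.3 to 0.37 × 17 = 6.3 participants per arm. The proposed count is therefore informative only as a comparison with placebo.

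**5. Orthostatic flag.** SAP 2.7.4.2 lists the parameters collected and names no positional reading. Protocol 8.4 describes sitting readings only. On these documents the flag has no data to act on.

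**The case against.** The strongest reply is that the listing was never meant to isolate a drug effect. The same section summarises change from baseline by arm against a randomised placebo group, with extremes, and the listing prints every value of a flagged sign, so baseline sits beside the flagged reading. This stands. A reader might infer that the vital-sign analysis cannot separate a drug effect from pre-existing hypertension, or that large individual changes are lost; the documents support neither. The limitation belongs to the flag read alone, plus the three gaps above.

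A reader might also cite a systolic fall from 165 to 100 mmHg as never notable. That does not follow. SAP 2.7.4.2 does not say whether pre-treatment values trigger the listing. If they do, 165 brings the participant in with all values shown. If they do not, as SAP 2.1.1 can be read, 100 alone crosses no limit. The weight example does not depend on this.

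It is also fair that the ECG layout is not a universal standard in this SAP, since laboratory data (SAP 2.7.3) have no count of notable values either. With 34 participants a listing can be read in full, and one participant in 17 is 5.9 percentage points, so any count will be imprecise. This limits the gain, but a pre-specified count still spares the reader an ad hoc classification.

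Finally, Protocol 8.4 leaves method detail to the Site Operations Manual, which is not available here. An empty orthostatic flag therefore shows neither that orthostatic hypotension was absent nor, conclusively, that posture was never varied.

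**Conclusion.** The point holds as a minor gap in descriptive safety reporting. The notable rule has no baseline reference and no count by arm, so it does not separate participants who newly cross a limit from those already beyond it. The existing change-from-baseline summaries cover much of the need, but not unscheduled values, temperature or counts of participants.

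The textual findings need no assumption. The size does: the 35-83% flagged and the 29-59% of those already above 140 at baseline rest on an assumed blood pressure distribution and on full follow-up in a study that was stopped early. It should not be stated as fact that the flag fires for most participants; at an assumed mean of 125 mmHg it fires for 35-46%. Error rates, power and the primary analysis are unaffected.

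**What to change.** In SAP 2.7.4.2, keep the listing and add one table by treatment: the number and percentage of participants with a newly notable post-baseline value, meaning not notable at baseline (as defined in SAP 2.1.1) and beyond the existing limit afterwards. Show high and low separately, state the denominator, use all scheduled, unscheduled and repeat post-baseline values as SAP 2.1.1 provides, and include temperature. Summarise weight also as percentage change from baseline. State whether pre-treatment values can trigger the listing.

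Reconcile the orthostatic wording in SAP 2.7.4.2 and Protocol 12.5.2 with Protocol 8.4. If the Site Operations Manual adds no standing or supine reading, delete the phrase or state that orthostatic change was not assessed.

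The cost is some SAP wording, one extra table and a weight summary from data already collected. If limits on the amount of change are added, they must be fixed before unblinded review.

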2.7.4.3 Suicidality assessment

C-SSRS data will be listed by treatment, participant, and visit/time; abnormalities will be flagged. Summary statistics will be provided by treatment and visit/time, if deemed relevant.

2.8 Pharmacokinetic endpoints

Agent serum concentration data will be listed by treatment, participant, and visit/sampling time point. Descriptive summary statistics will be provided by treatment and visit/sampling time point, Commercially Confidential Information

Summary statistics will include mean (arithmetic and geometric), SD, CV (arithmetic and geometric), median, minimum, and maximum. Commercially Confidential Information

Pharmacokinetic parameters will be listed by treatment and participant. Descriptive summary statistics will include mean (arithmetic and geometric), SD, and CV (arithmetic and geometric), median, minimum, and maximum. An exception to this is *Tmax* where median, minimum, and maximum will be presented, as applicable.

CSF to serum concentration ratio (expressed in %) will be calculated by the ratio of agent exposure in CSF to that in serum (for biotherapeutic agents) for post dose samples. The ratio will be calculated only if the collection dates of CSF and serum samples are on same day +/-2 days.

In cohort 1, Canakinumab concentrations will be assessed in serum and in CSF of all agent-treated participants. Serum and CSF PK samples will be collected at the timepoints defined in the PK/PD/IG Assessment Schedule (Predose before start of study treatment at screening visit and Day 85 in CSF and on Day 1 and Day 85 in serum). Any CSF samples having more than

500 red blood cells/ μ L will be documented, as such high cell counts may impact PK analysis. Concentrations of canakinumab in serum and CSF will be given in mass per volume units.

A previously utilized and validated mixed effects modeling approach may be used to characterize the exposure-related PK parameters (i.e., AUC and CL) of canakinumab. These results may be reported in a separate report.

2.9 PD and PK/PD analyses

The relationships between individual PK profiles or derived PK parameters and efficacy/PD measurements may be explored using graphical approaches (e.g., scatter plots) and regression analysis as appropriate.

Commercially Confidential Information

SAP Amendment 1

Commercially Confidential Information

Commercially Confidential Information

2.12 Interim analysis

Commercially Confidential Information

2.13 Data monitoring committee

This study will include an external Data Monitoring Committee (DMC). The DMC will function independently of site investigators participating in the study. The DMC will assess the progress of the EXPLAIN-AD treatment cohorts and the safety data. The Sponsor will continue, modify, or terminate investigational agents based on these reviews.

The analysis will be conducted by the trial statistician and programmer(s).

Specific details regarding composition, responsibilities, data monitoring, meeting frequency, and documentation of DMC reports, minutes, and recommendations are described in the Safety Surveillance Plan for each agent and the DMC Charter.

3 Sample size calculation

3.1 Primary endpoint(s)

For the primary endpoint, change in NTB total z-score at week 24, data from 36 evaluable participants per arm (investigational agent and placebo) provides $\sim\!80\%$ power to detect a statistically significant difference between the two groups at a 1-sided $\alpha\!=\!0.10$ when the true standardized mean difference is 0.5. The effect size of 0.5 corresponds a moderate treatment effect which is thought to represent a clinically meaningful improvement at 24 weeks. To account for 15% dropout rate, approximately n=86 participants randomized in a 1:1 ratio would be needed to address the primary objective. These calculations take into account results of the published study by Frölich et al. (2019), where the standard deviation of the change in NTB total z-score was estimated to be $\sim\!0.38$ for both active and placebo groups.

For smaller true effect sizes, the power is lower (Table 3-1 below).

Table 3-1 Sensitivity of power to changes in assumptions

SD (common to 2 arms)	True mean difference (Δ)	True effect size (Δ/SD)	alpha (1-sided)	Power
0.38	0.19	0.5	10%	80%
0.38	0.152	0.4	10%	66%
0.38	0.114	0.3	10%	50%
0.38	0.095	0.25	10%	41%

It is assumed that n=86 participants are randomized in a 1:1 ratio and the dropout rate is 15% (thus we have 72 evaluable participants, 36 per arm)

3.2 Secondary endpoint(s)

For the secondary endpoint, PET $^{\text{CCI}}$, a comparison between an investigational agent and placebo will be based on data from approximately 10 participants per arm. Assuming inter-participant variability of 20%-25%, the power to detect statistically significant treatment difference (using 1-sided α =-0.05) is shown in Table 3-2 below. For the 25% true mean reduction in microglial activation due to an anti-inflammatory agent vs. placebo, there is at least 87% power (assuming coefficient of variation is 25% or less).

Table 3-2 Power for treatment comparison using log-transformed PET CCI at week 12

Coefficient of variation (CV)	True mean reduction (active vs. placebo)	α (1-sided)	Power
0.2	30%	5%	99%
0.2	25%	5%	93%
0.2	20%	5%	78%
0.25	30%	5%	93%
0.25	25%	5%	81%
0.25	20%	5%	62%

The assumed sample size is n=20 (10 per arm)

4

Change to protocol specified analyses

The study was CCI stopped. Therefore, the IA planned after 24 patients complete PET TPSO at 24 weeks will not be conducted.

5 Reference

ICH E9(R1) Harmonized Guideline: addendum on estimands and sensitivity analysis in clinical trials to the guideline on statistical principles for clinical trials. Final version on 20 November 2019.
